8.8. Clinical Laboratory Evaluations

Clinical laboratory tests (hematology, serum chemistry, and urinalysis) will be performed at Screening, Check-in of Period 1 and at Check-out of Period 3 or Early Termination.

The serum chemistry profiles must be obtained under fasting conditions (approximately 10 h). Results of all laboratory tests will be included in the subject's eCRF.

The following clinical laboratory parameters will be evaluated:

- Serum chemistry (approximately 8.5 mL): sodium, potassium, magnesium, bicarbonate, chloride, calcium, inorganic phosphorus, AST, ALT, alkaline phosphatase, total bilirubin, glucose, creatinine, blood urea nitrogen, total protein, albumin, uric acid, creatine kinase, total cholesterol, and triglycerides.
- Hematology (approximately 4 mL): hemoglobin, hematocrit, red blood cell (RBC) count (with indices), reticulocyte count, white blood cell (WBC) count (with differential), and platelet count.
- Urinalysis: standard urinalysis, including a microscopic examination and specific gravity, pH, protein, glucose, ketones, blood, RBC, WBC, bilirubin, and urobilinogen.

Calculation of eGFR (using the Cockcroft-Gault equation) will be performed at Screening.

Tests for virology (HIV antibody, HBsAg, and HCV antibody) will be performed at Screening only.

Coagulation tests (PT/INR and aPTT) will be performed at Screening only. Approximately 2.7 mL of blood will be withdrawn for these tests.

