Plasma will be harvested and analyzed for pexidartinib using a validated liquid chromatography-tandem mass spectrometry (LC-MS/MS) method.

12-lead electrocardiograms (ECGs) will be performed at Screening, predose and at 2, 24 and 144 h postdose in each study period, at Check-out of Period 3 or Early Termination.

Vital signs (blood pressure, heart rate, oral temperature, and respiratory rate) will be performed at Screening, predose and at 2, 24, and 144 h postdose in each study period, at Check-out of Period 3 or Early Termination.

Clinical laboratory tests (hematology, serum chemistry, and urinalysis) will be performed at Screening, Check-in to Period 1, Day 7 of each period and at Check-out of Period 3 or Early Termination.

A physical examination will be performed at Screening, Check-in to Period 1 and check-out of Period 3 or Early Termination.

Adverse events and concomitant medication will be collected throughout the study.

Study Duration: Subjects will be screened no more than 21 d prior to dosing on Day 1 of Period 1.

The duration of the study (from Check-in to Check out) will be approximately 21 d.

Study Sites and Location: The study will be conducted in 1 clinical site, at Worldwide Clinical Trials in San Antonio, Texas, USA

Subject Eligibility Criteria: Subjects will be healthy males or non-childbearing potential females, 18 to 60 years (y) of age, inclusive and body mass index of 18 to 30 kg/m², inclusive.

Dosage Form, Dose and Route of Administration: Treatment A: Single oral 400 mg (2 × 200 mg capsules) of pexidartinib in the morning under fasting conditions with 240 mL of water

Treatment B: Single oral 400 mg (2 × 200 mg capsules) of pexidartinib with 240 mL of water in the morning within 30 min of a low-fat standard breakfast

	Treatment C: Single oral 200 mg (1 × 200 mg capsule) of pexidartinib with 240 mL of water in the morning within 30 min of a low-fat standard breakfast

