5. STUDY TREATMENT(S)

5.1. Assigning Subjects to Treatment Group(s) /Sequences and Blinding

5.1.1. Treatment Group(s) /Sequences

Subjects will be randomized to 1 of 6 sequences: ABC, ACB, BAC, BCA, CAB, and CBA.

The study treatments include:

- Treatment A: Single oral 400 mg (2 × 200 mg capsules) of pexidartinib in the morning with 240 mL of water after an overnight fast of 10 h
- Treatment B: Single oral 400 mg (2 × 200 mg capsules) of pexidartinib in the morning within 30 min of a low-fat standard breakfast meal
- Treatment C: Single oral 200 mg (1 × 200 mg capsule) of pexidartinib in the morning within 30 min of a low-fat standard breakfast meal

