The following procedures will be performed on Day 4 of each period:

- Blood samples for PK analysis at 72 and 84 h postdose
- Continuous monitoring of AEs and concurrent medication

6.4.6. Day 5

The following procedures will be performed on Day 5 of each period:

- Blood samples for PK analysis at 96 and 108 h postdose
- Continuous monitoring of AEs and concurrent medication

6.4.7. Day 6

The following procedures will be performed on Day 6 of each period:

- Blood samples for PK analysis at 120 and 132 h postdose
- Continuous monitoring of AEs and concurrent medication

6.4.8. Day 7

The following procedures will be performed on Day 7 of each period:

- Vital signs (blood pressure, heart rate, oral temperature and respiratory rate) at approximately 144 h postdose
- 12-lead ECGs at approximately 144 h postdose
- Blood sample for PK analysis at 144 h postdose
- Continuous monitoring of AEs and concurrent medication

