6.6. Check-out or Early Termination

The following procedures will be performed at check-out of Period 3 (Day 7) or upon Early Termination:

- Complete physical exam
- Body weight
- Vital signs (blood pressure, heart rate, oral temperature, and respiratory rate), if not already taken
- 12-lead ECGs, if not already taken
- Blood samples for:
 - Clinical laboratory tests (hematology and fasting serum chemistry); subjects will fast for approximately 10 h prior to check-out for the serum chemistry tests
 - Serum pregnancy test for all females
- Urine samples for clinical laboratory urinalysis tests
- Continuous monitoring of AEs and concurrent medication

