8.9. Vital Signs

Resting vital signs will be taken after at least 10 min in a supine position.

Resting vital signs (blood pressure, heart rate, oral temperature, and respiratory rate) will be performed at Screening, predose and at 2, 24, and 144 h postdose in each study period, or Early Termination.

When vital signs measurements and a blood draw are scheduled for the same time point, the vital signs should be taken within approximately 5 min prior to the blood draw. Predose vital signs measurements will be taken within 2 h prior to the dose.

Body weight and height will be recorded at Screening. Body weight will also be recorded at Check-in to Period 1 and at Check-out of Period 3 or Early Termination. BMI will be calculated at Screening.

Information will be entered in the CRF on whether or not measured, date of measurement, and measurement results for the following items: systolic blood pressure, diastolic blood pressure, pulse, respiratory rate, body temperature, height, body weight, and BMI.

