10.4.3.2. Clinical Laboratory Evaluation Analyses

Hematology, serum chemistry, and urinalysis, at each planned assessment will be summarized for the safety analysis set by treatment. Shift tables (CTCAE grade of the worst value) will also be provided by treatment. Subjects with abnormal values will be noted in the data listings.

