16.2. Blood Collection Volume by Category and Total

Table 16.1: Blood Collection Volumes

Test		Volume per Test (mL)	No. of Time Points per Subject	Total Volume per Test (mL)	
Screening	Serum chemistry, HIV antibody, HBsAg, HCV antibody, FSH if applicable, serum pregnancy	8.5	1	8.5	
	Hematology	4.0	1	4.0	
	Coagulation (PT/INR and aPTT)	2.7	1	2.7	
Serum chemistry, serum pregnancy, if applicable		8.5	2	17.0	
Hematology		4.0	2	8.0	
PK pexidartinib			2.0	91	182.0
Total:			-	95	222.2

Abbreviations: aPTT = activated partial thromboplastin time; FSH = follicle stimulating hormone; HBsAg = hepatitis B surface antigen; HCV = hepatitis C virus; HIV = human immunodeficiency virus; INR = international normalized ratio; PK = pharmacokinetic; PT = prothrombin time

Notes: Blood collection in subjects with adverse events should be continued until resolution of the events (even after the scheduled observation period). Blood collection to be used for several different tests but taken at one time is counted as one collection.

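### Synopsis and body disagree on the safety laboratory schedule; if the body is followed, the by-treatment laboratory tables rest on one value per completer, taken after Period 3

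*Combined protocol and SAP*

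**What the plan says.** The synopsis (Study Design) lists hematology, serum chemistry and urinalysis at "Screening, Check-in to Period 1, Day 7 of each period and at Check-out of Period 3 or Early Termination".

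Section 8.8 has no Day 7 panel: "Clinical laboratory tests (hematology, serum chemistry, and urinalysis) will be performed at Screening, Check-in of Period 1 and at Check-out of Period 3", or at Early Termination. Three other places in the body match it:

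- Section 6.4.8 (Day 7 of each period) lists vital signs, ECG and "Blood sample for PK analysis at 144 h postdose", with AE and medication monitoring, but no safety laboratory tests.
- Section 6.6 puts the laboratory tests at Period 3 check-out or Early Termination, where "subjects will fast for approximately 10 h prior to check-out for the serum chemistry tests".
- Table 16.1 (Section 16.2) budgets two draws after screening, in the row "Serum chemistry, serum pregnancy, if applicable" and again in the hematology row.

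Vital signs are treated differently. Section 8.9 schedules them "predose and at 2, 24, and 144 h postdose in each study period", and Section 6.4.8 places both vital signs and ECGs at 144 h in every period.

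For analysis, Section 10.4.3.2 summarizes laboratory data by treatment at each planned assessment and adds: "Shift tables (CTCAE grade of the worst value) will also be provided by treatment". Section 10.1 keeps unscheduled and repeat assessments out of the descriptive statistics.

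**The concern.** Tables by treatment need a post-dose value that belongs to each treatment. The synopsis schedule supplies one per period. The body schedule supplies a completer with one in total, after the third dose. That value can be assigned at most to the Period 3 treatment, and the worst value in the shift table is simply that value. All three treatments would appear in the tables, but from different subjects, so the within-subject crossover becomes a small between-subject comparison.

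The secondary objective (2.1.2) is to characterize safety with low-fat food and without food, laboratory tests are a named safety endpoint (2.3.2), and the one event of special interest (8.3) is defined by bilirubin with ALT or AST. An enzyme rise without symptoms is found only if blood is drawn. Under the body schedule no panel is planned between dose 1 and Period 3 check-out.

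A lesser point: Section 10.4.3.1 says which treatment a washout AE counts toward, while 10.4.3.2 gives neither an attribution rule nor a baseline for laboratory values.

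**Working it through.** **1. Which schedule does the blood budget follow?** Inputs from Table 16.1: screening 8.5 + 4.0 + 2.7 mL; each later panel 8.5 mL (chemistry) + 4.0 mL (hematology); 91 PK samples of 2.0 mL. With k panels after screening:

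Volume = 15.2 + 12.5k + 182.0

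- k = 2 (check-in and check-out): 15.2 + 25.0 + 182.0 = **222.2 mL**, exactly the stated total.
- k = 4 (check-in and Day 7 of Periods 1, 2 and 3, the last serving as check-out): 15.2 + 50.0 + 182.0 = **247.2 mL**.

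The budget was therefore built on the body schedule. The PK count of 91 fits 31 samples × 3 periods = 93, less 2 if the 144 h sample of Periods 1 and 2 also serves as the next predose sample.

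**2. Who informs each treatment under the body schedule?** Section 5.1.1: "Subjects will be randomized to 1 of 6 sequences: ABC, ACB, BAC, BCA, CAB, and CBA". By last treatment:

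| Last treatment | Sequences | Share |
|---|---|---|
| A (400 mg, fasted) | BCA, CBA | 2 of 6 |
| B (400 mg, fed) | ACB, CAB | 2 of 6 |
| C (200 mg, fed) | ABC, BAC | 2 of 6 |

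Section 10.5 gives 24 randomized and at least 21 expected to complete. Equal allocation, 24/6 = 4 per sequence, is an assumption.

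- All 24 complete: 24 × 2/6 = 8 per treatment.
- 21 complete: 21 × 2/6 = 7 on average. Each treatment starts with 8 and can lose 0 to 3 of the 3 dropouts, so the range is 5 to 8.
- By meal state among 21: last dose fed 21 × 4/6 = 14 (range 13 to 16), fasted 7 (range 5 to 8).

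**3. Coverage among 21 completers**

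| | Body | Synopsis |
|---|---|---|
| Post-dose panels per completer | 1 | 3 |
| Subject-by-treatment cells filled (21 × 3 = 63) | 21 | 63 |
| Completers with separate panels after A and after B | 0 | 21 |

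To show what this does to the information: if no subject on a treatment had an abnormality, the one-sided 95% upper limit for its frequency is 1 − 0.05^(1/n). That is 35% for n = 7 and 13% for n = 21.

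**4. Timing and carry-over.** With doses s days apart, the check-out panel falls 2s + 6 days after dose 1 and s + 6 days after dose 2. For s = 6 that is 18 and 12 days; for s = 7, 20 and 13 days. Taking the 27 h half-life (1.2.1.4) and assuming one-phase decline, the fraction of drug left is 2^(−144/27) = 2.5% at 144 h and 2^(−288/27) = 0.06% at 12 days. Residual drug is negligible. Earlier doses could confound the panel only through laboratory effects that outlast the drug.

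**The case against.** The contradiction itself is hard to dispute. The case on the other side is about its weight.

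- **Small impact.** There is no hypothesis (2.2), and the objective is to characterize safety, not to compare treatments. AEs, vital signs and ECGs are collected in every period. Laboratory abnormalities judged to be AEs are tabulated by treatment. The liver events in 8.3 arose under continuous multiple dosing, and prior single doses reached 2400 mg. All of this stands and keeps the point at the low end. It does not cover an abnormality in Period 1 or 2 for which no blood was drawn. A Day 7 panel can also miss a rise that resolves within 6 days.
- **Safety set, not completers.** The tables use everyone dosed, and a withdrawn subject has an Early Termination panel. True: with 3 dropouts, the panels following a given treatment could then number 5 to 11. Each dropout adds at most one panel, so at most 24 of 72 planned cells are filled, still one third.
- **Confounding is speculative.** Largely accepted, as the half-life calculation shows. The thin, between-subject tables do not depend on it.
- **Baseline and attribution.** A pre-drug baseline is not a defect in itself, vital signs and ECGs have the same silence on these rules, and a SAP still to be finalized (10.6) may supply them. This part is ancillary. A SAP can define rules, but it cannot supply panels that were not drawn.
- **Four body locations outvote one synopsis sentence.** This makes the body the likelier practice at the site. In that case the by-treatment tables in 10.4.3.2 do not fit the data that will be collected.

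**Conclusion.** The concern holds. The synopsis gives three post-dose laboratory panels per completer and the body gives one, with no rule for which governs. If the body governs, about 7 of 21 completers (range 5 to 8) inform each treatment, one third of the planned cells are filled, and no completer has both a fed and a fasted panel. If the synopsis governs, the data gap disappears, but Sections 6.4.8 and 8.8 and Table 16.1, which the site will work from, are wrong.

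The contradiction needs no assumption. The counts assume 4 subjects per sequence and 3 dropouts. Table 16.3 lost its column layout in the text available; its single laboratory mark appears to sit under check-out, but the conclusion does not rely on it. The PK endpoints are unaffected. This should be fixed, at the low end of priority.

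**What to change.** **Preferred, matching the synopsis.**

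- Add a Day 7 (144 h) panel in Periods 1 and 2 to Sections 6.4.8 and 8.8 and Table 16.3, with Period 3 Day 7 serving as check-out.
- With 6-day spacing, draw it on the next dosing morning before any test breakfast and before the dose; the existing 10 h fast covers it. With 7-day spacing, draw it before breakfast after an overnight fast.
- In Table 16.1 raise the post-screening draws from 2 to 4: chemistry 4 × 8.5 = 34.0 mL, hematology 4 × 4.0 = 16.0 mL, total 247.2 mL.
- In Section 10.4.3.2 state that each Day 7 panel counts toward that period's treatment, and name the shift-table baseline: Period 1 check-in throughout, or the preceding Day 7 panel for Periods 2 and 3.

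Cost: two more panels and 2 × 12.5 = 25 mL of blood per subject, in subjects who are confined and already bled at 144 h, plus text alignment.

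**If the body schedule was intended.** Delete the Day 7 laboratory tests from the synopsis and replace the by-treatment laboratory tables with one overall check-in to check-out shift table. This costs text changes only, but gives up laboratory information by treatment.

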8.9. Vital Signs

Resting vital signs will be taken after at least 10 min in a supine position.

Resting vital signs (blood pressure, heart rate, oral temperature, and respiratory rate) will be performed at Screening, predose and at 2, 24, and 144 h postdose in each study period, or Early Termination.

When vital signs measurements and a blood draw are scheduled for the same time point, the vital signs should be taken within approximately 5 min prior to the blood draw. Predose vital signs measurements will be taken within 2 h prior to the dose.

Body weight and height will be recorded at Screening. Body weight will also be recorded at Check-in to Period 1 and at Check-out of Period 3 or Early Termination. BMI will be calculated at Screening.

Information will be entered in the CRF on whether or not measured, date of measurement, and measurement results for the following items: systolic blood pressure, diastolic blood pressure, pulse, respiratory rate, body temperature, height, body weight, and BMI.

8.10. Electrocardiograms

ECGs will be read on site as part of the safety assessments.

12-lead ECGs will be performed at Screening, predose, and at 2, 24 and 144 h postdose, or Early Termination.

Subjects should be lying quietly in a fully supine position for at least 10 min prior to each 12 lead ECG recording.

When a blood draw is scheduled concomitantly with an ECG, the ECG should be taken within 10 min prior to the blood draw. Predose ECGs will be taken within 2 h prior to the dose.

8.11. Physical Examinations

A complete physical examination will be performed at Screening. A complete physical examination will be performed at Check-in to Period 1 and at check-out of Period 3 or Early Termination. A medically qualified person will perform the physical exam. The physical examination will include the examination of the following body systems: respiratory, cardiovascular, gastrointestinal, dermatological, musculoskeletal, psychiatric, neurologic, and head, eyes, ears, nose, and throat.

8.12. Drug and Alcohol Screen

A urine screen for alcohol, cotinine, and drugs of abuse will be performed for all subjects at Screening and at Check-in. Alcohol, cotinine, amphetamines, barbiturates, benzodiazepines, cocaine, opiates, phencyclidine and cannabinoids will be included in the assay.

8.13. Pregnancy Test

For all female subjects, serum pregnancy tests will be performed at Screening, Check-in to Period 1 and Check-out of Period 3 or Early Termination. Dosing on Day 1 of Period 1 will be contingent upon a negative result.

8.14. Serum FSH

At Screening, should a female subject report postmenopausal status not induced by surgical sterilization, a serum FSH measurement will be obtained.

8.15. Other Examinations

Not applicable.

9. OTHER ASSESSMENTS

Not applicable

10. STATISTICAL METHODS

10.1. General Statistical Considerations

All PK and safety data obtained in this study will be displayed in data listings and summarized using descriptive statistics.

Categorical data will be presented in contingency tables with cell frequencies and percentages for the subject population.

Extra measurements (such as unscheduled or repeat safety assessments) will not be included in the descriptive statistics, but will be included in subject listings.

10.2. Analysis Sets

10.2.1. Pharmacokinetic Analysis Set

The PK analysis set includes all subjects who receive at least 1 dose of pexidartinib and have sufficient samples to adequately assess the PK parameters. The impact of clinically significant events that may affect the estimation of PK parameters will be assessed while analyzing data and handled appropriately. Any exclusion will be clearly delineated in the report. Individual plasma concentrations for all subjects will be reported.

10.2.2. Safety Analysis Set

The safety analysis set includes all subjects who receive at least 1 dose of pexidartinib.

10.3. Study Population Data

The safety analysis set will be summarized for demographic characteristics. Continuous demographic variables (age [calculated from date of birth to the date of when the ICF was signed], weight, height, and BMI) for all subjects will be summarized with descriptive statistics. Categorical demographic variables (sex, race, and ethnicity) will be summarized with frequency counts and corresponding percentages.

Medical history data will also be summarized.

10.4. Statistical Analysis

10.4.1. Pharmacokinetic Analyses

All PK analyses will be based on the PK analysis set.

Individual plasma concentration-time data will be presented graphically by treatment and actual time points using linear and semilog scales. Mean (SD) plasma concentration-time data will be presented graphically for pexidartinib by nominal time points using linear and semi-log scales.

If a subject vomits within a period of time equal to two times the median Tmax of pexidartinib, statistical analysis will be performed with and without data from the period subject vomited in.

Log-transformed Cmax, AUClast, and AUCinf of pexidartinib will be analyzed using a mixed effect analysis of variance (ANOVA) model with treatment, period, and sequence as fixed effects and subject nested within sequence as a random effect. The point estimates of ratios of central values for Treatments B versus A, will be calculated by exponentiation of the differences in the least squares means (logarithm-transformed data) between the treatments, Treatment B (400 mg pexidartinib administered with a low-fat meal) versus Treatment A (Reference, 400 mg pexidartinib in the fasted state). The 2-sided 90% confidence intervals (CIs) will be calculated similarly by exponentiation of the corresponding 2 sided 90% for the difference between the least squares means calculated for the ln transformed values.

A more detailed description of the planned pharmacokinetic analysis will be provided separately in the SAP.

10.4.2. Pharmacodynamic Analyses

Not applicable.

10.4.3. Safety Analyses

All safety analyses will be based on the safety analysis set.

10.4.3.1. Adverse Event Analyses

Adverse events will be coded using the Medical Dictionary for Regulatory Activities (MedDRA) coding dictionary. All AEs including serious AEs will be mapped to system organ class and preferred term and will be listed in the data listing.

A TEAE is defined as an AE that emerges during treatment, having been absent pre-treatment, or worsens relative to the pre-treatment state. The number and percentage of subjects reporting TEAE will be tabulated for the safety set by MedDRA system organ class and preferred term with a breakdown by treatment, and further by relationship (related / not related) to study drug administered and by Common Terminology Criteria (CTC) AE grade.⁵ An AE that emerges or worsens in severity during a washout period will be counted as a TEAE toward the treatment in the preceding period. Listings of deaths, SAEs, and AEs that lead to discontinuation of a subject will be presented.

